> **TABLE OF FIGURES**

Figure 1: 11

Figure 2: 11

Figure 3: 11

Figure 4: Two examples of how to make corrections in the CRF 21

> **SYNOPSIS OF THE EVALUATION**

Objective

[figure not shown]
The aim of this evaluation is to investigate the ability of newly developed adhesive patches to absorb moisture. The primary objective is:

- To investigate the ability of different adhesives to absorb moisture in the adhesive layer closest to skin and within the adhesive layer, using an electronic sensor system.

Primary endpoint:

Resistance assessed by a sensors system including time for passing pre-defined resistance thresholds for individual sensors.

Pass/fail criteria

No formal success criteria are applied in this pilot evaluation. The study will provide valuable insight into the performance of adhesives when exposed to output and/or sweat.

Design of the investigation

Overall:

- Single arm. Open-labelled, not randomized
- Controlled

Completion/Termination visit (can be done by phone). At the test visits, the subjects will be exposed up to 2 adhesive patches

Population

The population consists of subjects who comply with the following inclusion criteria and do not comply with the following exclusion criteria:


Inclusion criteria for [REDACTED] Healthy volunteers:
 
1. Have given written informed consent2. Be at least 18 years of age and have full legal capacity3. Have intact skin on the area used in the evaluation4. Have an abdominal area accessible for application of test product (assessed by investigator)5. Negative pregnancy test for fertile women6. Signed document claiming use of safe contraceptives for fertile women	
1. Currently receiving or have within the past 2 month received radio- and/or chemotherapy2. Currently receiving or have within the past month received topical steroid treatment in the peristomal skin area or systemic steroid (tablet/injection) treatment.3. Are pregnant or breastfeeding4. Having dermatological problems in the peristomal- or abdominal area (assessed by investigator)5. Participating in interventional clinical investigations or have previously participated in this evaluation. Exception: Participation in other Coloplast sponsored clinical investigations or evaluations is accepted under the circumstances that the subject has paused the activities in the investigation/evaluation and are otherwise complying with the inclusion and exclusion criteria of this (CP284) Evaluation
--	---

Test products

A range of different newly developed adhesive patches embedded with sensors will be tested in this evaluation to assess the moisture absorption capabilities of the adhesive.

Test products can be applied in combination with CE-marked accessories

The test product is not considered a medical device.

Investigation approval

The Evaluation will be approved by the Ethics Committee in Denmark before initiation.

> LIST OF ABBREVIATIONS

ABBREVIATION	WRITTEN OUT	EXPLANATION
AE	Adverse Event	See section 13.1
CRF	Case Report Form	
CM	Clinical Manager	Coloplast study operational responsible and author of this Evaluation
DQF	Data Query Forms	A DQF is a query specifically used in clinical research. The DQF is the primary data query tool from the sponsor to clarify discrepancies and ask the investigator for clarification. The DQF is part of the data validation process in a clinical investigation.
EC	Ethics Committee	

1.2. Sponsor representatives

SENIOR STATISTICIAN	HEAD OF CLINICAL OPERATIONS
[REDACTED]	
SENIOR MEDICAL AFFAIRS PROJECT MANAGER	SCIENTIFIC MANAGER
[REDACTED]	
CLINICAL MANAGER	MEDICAL ADVISOR
[REDACTED]	

In case of emergency, please contact the Clinical Manager from the above list of sponsor representatives.

2. Identification and description of the material

The test product (see Figure 2 and 3) is not considered a medical device, but a range of different, newly developed adhesive strips

3. Justification for the conduct of the Evaluation

The present evaluation investigates the ability of different adhesives to absorb moisture in the adhesive layer closest to skin and within the adhesive layer, using an electronic sensor system.

4. Ethical Considerations, risks and benefits

The evaluation is conducted in accordance with current law and applicable standards see section 11.

The rights, safety and well-being of human subjects will prevail over interest of science and society.

All adhesives will undergo risk assessment and biological safety evaluations before initiation of the evaluation and therefore, the risks are considered to be equal to the use of ostomy products already on the market. Risks associated with the use of ostomy products are skin irritation and mechanical trauma.

The evaluation is conducted in accordance with 'The Declaration of Helsinki', 1964, last amended at the 64th WMA General Assembly, Fortaleza, October 2013, and as far as possible in compliance with the ISO 14155 considering the nature of the investigation not investigating a medical device. The participating subjects will contribute with important information for developing new ostomy products that may reduce leakage and the risk and disadvantages for participating is estimated to be low.

5. Objectives of the evaluation

5.1. Objective

The primary objective is:

- To investigate the ability of different adhesives to absorb moisture in the adhesive layer closest to skin and within the adhesive layer, using an electronic sensor system.

5.2. Risks and anticipated adverse device effects to be assessed

Each type of adhesives will undergo risk assessment and biological safety evaluations before application and therefore, the risks are considered to be equal to the use of ostomy products already on the market. Risks associated with the use of ostomy products are skin irritation and mechanical trauma.

[figure not shown]
6. Design of the Evaluation

6.1. General

The pilot evaluation is based on an open explorative design evaluating the impact that moisture has on newly developed adhesives materials.

Overall:

- Single arm. Open-labelled, not randomized
- Controlled

Baseline visit:

At the baseline visit, the subjects are included in the evaluation and baseline information is collected.

Test visits:

The test product will be applied by trained study personnel. Each subject can wear up to 6 test products at the time ([Figure 1: Placement of test product](#))

[figure not shown]
During a test visit the adhesive patch may be deliberately exposed to moisture e.g. by subjects doing exercise on a spinning cycle or taking a shower.

[figure not shown]
6.1.1. Primary end points

Resistance assessed by a sensors system including time for passing pre-defined resistance thresholds for individual sensors.

[figure not shown]

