6.4. Procedures

6.4.1. Evaluation-related procedures

Before initiation of the evaluation, sponsor must be provided with key personnel's signed and dated curriculum vitae (not more than 2 years old) to verify their qualifications. Key site personnel are those who treat or evaluate subject data in the evaluation. Also, the sponsor will ensure that all site personnel are trained in the evaluation procedures, how to complete the CRFs, procedure for reporting an adverse event or serious adverse event (how, when, to whom), and who to contact in case of emergency [REDACTED]

Information visit:

[figure not shown]
At the information visit, oral and written information about the evaluation is given by the PI or his/her representative and the subjects are given the opportunity to ask questions about the evaluation (Informed consent process section 12). Subjects can continue to Baseline visit the same day - If practical possible.

[figure not shown]
In case pre-stripping of the abdominal skin (not peristomal skin) is required, subjects will be instructed how to do this. Pre-stripping is done to remove dead skin cells and grease in the outer skin layer and must be done 3 days prior to test visit. If pre-stripping is requested, it will be done with a CE-marked adhesive material.

Baseline visit:

At the Baseline visit, following documents will be collected:

1. Signed Informed Consent Form
2. Signed Informed Consent Form - Interview
3. Signed Secrecy consent
4. Pregnancy test for fertile women and document claiming use safe contraceptives

Completion/Termination visit:

- Subject will visit site for study completion and termination (visit can also be done by phone)
- Subjects that can/will not complete the test period will proceed to the termination visit.
- If the subject experiences skin complications during the test period, the investigator/study nurse will evaluate the skin condition to decide whether subject can complete the test.

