6.5.1. Source data verification

In this study the following is considered source data:

- Informed Consent Form
- Informed Consent Form – Interview
- Electronic resistance/time curve
- CRF

All data will be collected using an CRF. The investigator is responsible for entering all data and only data referred to in this evaluation plan will be recorded in the CRF.

Data points for data verification:

- Informed Consent Forms
- In- / Exclusion criteria
- Pregnancy test
- Concomitant medication(s)
- Concomitant disease(s)
- AE/ADE

The informed consent forms will be 100% verified for timely completeness.

All CRF will be 100% verified for completeness.

Only the investigator, delegated site personnel and the sponsor representatives will have access to all the CRFs. The subject will have access to his/her own CRF.

7. Statistical considerations

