7.1. Statistical design, method and analytical procedures

7.2. Sample size

This is a pilot evaluation of adhesives under development.

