7.3. Level of significance and power

The data will primarily be evaluated based on summary statistics and listings of data from cohort. If explorative statistical analyses are performed a significance level of 5% will be applied.

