7.4. Pass/fail criteria

No formal pass/fail criteria are applied in this explorative pilot evaluation.

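### Does the lack of a visible rule for sensors that never pass the resistance threshold distort the comparison of adhesives?

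*Combined protocol and SAP*

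**What the plan says.** The primary endpoint in section 6.1.1 is "Resistance assessed by a sensors system including time for passing pre-defined resistance thresholds for individual sensors". It has two parts: the resistance reading itself, and the time at which each sensor passes set thresholds. The objective in section 5.1 concerns different adhesives and two positions, next to the skin and inside the adhesive layer.

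On analysis, section 7.3 states: "The data will primarily be evaluated based on summary statistics and listings of data from cohort". It adds: "If explorative statistical analyses are performed a significance level of 5% will be applied". On size, section 7.2 says only: "This is a pilot evaluation of adhesives under development". Section 7.4 says: "No formal pass/fail criteria are applied in this explorative pilot evaluation".

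Two other places bear on the point. Section 6.4.1 foresees early stopping: "Subjects that can/will not complete the test period will proceed to the termination visit". Section 6.5.1 lists the "Electronic resistance/time curve" among the source data.

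Section 7.1, on statistical design and method, shows a heading with no text. The numbering skips 6.1.2 and 7.5, the Table 1 flow chart has no column for test visits, and section 7.7 refers to a statistical analysis plan.

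**The concern.** Time to a threshold is a time-to-event measure. A sensor still below its threshold when the patch is removed or the subject stops has no crossing time; it is known only to exceed the time observed. Such sensors are a realistic prospect. Section 6.1 makes deliberate moisture exposure optional, moisture may reach sensors inside the layer late or not at all, and early stopping is foreseen.

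If these sensors were left out, the loss would depend on the property being measured: the slower the moisture, the more sensors are dropped. A crosser-only mean cannot exceed the wear time, so quite different adhesives could look alike. If wear times also differed between adhesives, the ranking could turn round. In a pilot meant to guide development, that ranking is a main product.

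**Working it through.** The documents give no sample size, wear time, threshold or crossing rate, so there is no figure of theirs to reproduce. The check asks how large the effect would be under assumed values, and then whether the plan commits to the analysis that produces it.

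**Assumed inputs.** Crossing times are exponential with mean m, and every sensor is worn for a time T. Adhesive A has m = 2 h and adhesive B has m = 8 h (true ratio 4).

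**Formulas.**
- Share crossing: 1 − exp(−T/m)
- Mean among crossers: m − T/(exp(T/m) − 1)
- Restricted mean to T: m(1 − exp(−T/m))
- Median over all sensors: m ln 2, estimable when more than half cross

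**Example at T = 2 h.**
- A: 2 − 2/(e − 1) = 0.84 h
- B: 8 − 2/(exp(0.25) − 1) = 0.96 h

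| T | Share crossing A / B | Crosser-only mean A / B | Ratio | Restricted mean A / B | Ratio |
|---|---|---|---|---|---|
| 2 h | 63% / 22% | 0.84 / 0.96 h | 1.15 | 1.26 / 1.77 h | 1.40 |
| 4 h | 86% / 39% | 1.37 / 1.83 h | 1.33 | 1.73 / 3.15 h | 1.82 |
| 8 h | 98% / 63% | 1.85 / 3.34 h | 1.81 | 1.96 / 5.06 h | 2.58 |

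**Unequal wear.** With B worn 2 h and A worn 4 h, the crosser-only means are 0.96 h and 1.37 h, so the slower adhesive looks faster. The shares crossing, 22% and 86%, still point the right way.

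**Dependence on the crossing rate** (exponential, true ratio 2). The crosser-only ratio is 1.79 when 99.9% and 97% of sensors cross, 1.35 at 95% and 78%, 1.17 at 80% and 55%, and 1.09 at 60% and 37%. With Weibull shapes 2 and 3 and 80% of the faster group crossing, it is 1.14 and 1.12. The direction is general. The size ranges from small to severe with inputs that the documents do not give.

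**Is that the planned analysis?** Section 7.3 names no mean and no restriction to crossers. The following all count as summary statistics:
- The percentage crossed shows the difference directly (63% against 22% at 2 h).
- Medians need not leave anyone out. In a common window non-crossers rank above all crossers, so the median is valid once more than half cross. At T = 8 h the medians are 2 ln 2 = 1.39 h and 8 ln 2 = 5.55 h, which gives the true ratio of 4. At T = 4 h, B's median would be reported as not reached.
- Kaplan-Meier quantiles do the same where wear times vary.

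The listings would also show which sensors have no crossing time.

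**Can the rule be settled later without loss?** The resistance/time curve is source data. Crossing and end of recording can both be read from it, and a sensor that never crosses still contributes its resistance to the endpoint.

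**The case for a change.** The strongest case for a change is that it costs a sentence. Summary statistics is a loose term that permits crosser-only means, and nothing visible prevents them. Non-crossing is likely enough to plan for, and describing how adhesives differ is the purpose of the study. A rule fixed in advance would also stop the summary being chosen after the curves are seen.

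Part of this stands. The visible text does leave the rule open, and a crosser-only mean would be a poor summary whenever a sizeable share of sensors does not cross. An analyst should report the percentage crossed by a fixed time, with Kaplan-Meier quantiles or a restricted mean to a common cut-off, and should allow for several sensors and patches per subject in any interval or test.

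It does not amount to a fault in the plan. Permitting a poor summary is not planning one. The obvious remedies also have limits. The restricted mean at 4 h gives a ratio of 1.82 against an assumed 4. Treating detachment as ordinary censoring assumes that it is unrelated to moisture, which is doubtful for a wetted adhesive. Starting the clock at exposure fails where no deliberate exposure takes place. The ranking reversal needs wear times that differ systematically by adhesive, which no section indicates. Finally, a rule may already stand in text that is not visible, in section 7.1 or in the statistical analysis plan that section 7.7 mentions.

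**Conclusion.** No change to the plan follows. The gap is an unstated handling rule that a competent analyst fills from data already being kept. Crosser-only averaging could shrink a true ratio of 4 to between 1.15 and 1.81 under the assumed exponential times and 2 to 8 h of wear, but the plan does not call for it. With nearly all sensors crossing, the distortion would be small. The documents do not allow the actual size to be judged.

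No error rate or decision rule depends on the point: there is no confirmatory test, and the 5% level applies only to optional exploratory analyses. The conclusion assumes that the full curves are retained, as section 6.5.1 implies, and that the report gives the number of sensors behind each time summary.

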6.1.3. Rationale for selection and measurement of end points

Leakage is one of the greatest concerns for people with an ostomy. The frequency of leakage correlates to the degree of peristomal skin complications; therefore, ostomy appliances with better ability to reduce leakage have the potential of improving the peristomal skin condition and quality of life. Constant evaluation and development of new ostomy appliances is therefore of high importance and clinically relevant.

6.2. Test products and comparator(s)

[figure not shown]
The test products will be newly developed adhesives. The evaluation does not include comparator devices.

6.3. Subjects

To be included in the evaluation, the subjects must comply with the selection criteria described in section 6.3.1 and must not comply with criteria described in 6.3.2.

6.3.1. Inclusion criteria for subject selection

Subjects interested in participating the evaluation must comply with the following criteria:

Inclusion criteria for healthy volunteers [REDACTED]

1. Have given written informed consent
2. Be at least 18 years of age and have full legal capacity
3. Have intact skin on the area used in the evaluation
4. Have an abdominal area accessible for application of test product (assessed by investigator)
5. Negative pregnancy test for fertile women
6. Signed document claiming use of safe contraceptives for fertile women

6.3.2. Exclusion criteria for subject selection

Subjects complying with the following criteria must be excluded from participation in the evaluation:

1. Currently receiving or have within the past 2 month received radio- and/or chemotherapy

2. Currently receiving or have within the past month received topical steroid treatment in the peristomal skin area or systemic steroid (tablet/injection) treatment.
3. Are pregnant or breastfeeding.
4. Having dermatological problems in the peristomal- or abdominal area (assessed by investigator)
5. Participating in interventional clinical investigations or have previously participated in this evaluation.
Exception: Participation in other Coloplast sponsored clinical investigations/evaluations is accepted under the circumstances that the subject has paused the activities in the investigation/evaluation and are otherwise complying with the inclusion and exclusion criteria of this (CP284) Evaluation

Inclusion 5, 6, 7 and Exclusion 3: Women are considered fertile if they have had a least one period during the last 12 months. Besides a negative pregnancy test the women must also sign a document claiming that they will use safe contraceptives during the study period (i.e. contraceptive coil, hormone based contraceptives or surgical sterilization). However, in some cases when females older than 50 years but not yet post-menopausal, the investigator may evaluate that it is not reasonable to ask these females to start using safe contraceptives for the duration of the investigation (e.g. if the subject is abstinent, the partner is surgically sterilized, or either subject or partner is infertile). In these cases, the investigator can include the females, but has a responsibility of ensuring that he/she has done what he/she can to prevent these subjects from becoming pregnant. As a minimum, the investigator, must talk to the females about the risk of and how to avoid unwanted pregnancy at inclusion and at every visit hereafter.

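### No exclusion criterion covers a known allergy or earlier reaction to skin adhesives, so a volunteer with that history and currently intact skin is eligible

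*Combined protocol and SAP*

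**What the plan says.** Section 6.3 makes the listed criteria decide eligibility: subjects "must comply with the selection criteria described in section 6.3.1 and must not comply with criteria described in 6.3.2".

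Two criteria concern the condition of the skin:

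- Inclusion 3 (section 6.3.1): "Have intact skin on the area used in the evaluation".
- Exclusion 4 (section 6.3.2): "Having dermatological problems in the peristomal- or abdominal area (assessed by investigator".

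The other four exclusions concern recent radio- or chemotherapy, recent steroid treatment, pregnancy or breastfeeding, and participation in other studies or earlier participation in this one. The synopsis repeats the same five.

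On exposure, section 6.2 says "The test products will be newly developed adhesives". Section 6.1 says "Each subject can wear up to 6 test products at the time", whereas the synopsis says "At the test visits, the subjects will be exposed up to 2 adhesive patches". Section 6.4.1 adds a possible preparation step on the abdominal skin: "If pre-stripping is requested, it will be done with a CE-marked adhesive material". The synopsis also allows CE-marked accessories alongside the test products.

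On risk, sections 4 and 5.2 carry the same statement: "Risks associated with the use of ostomy products are skin irritation and mechanical trauma". Both sections consider the risks equal to those of marketed ostomy products. Only section 4 goes on to describe the risk of taking part as low.

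**The concern.** Adhesive contact with skin is the whole of the exposure in this evaluation, and the adhesives are new. A person who already knows that adhesives have irritated or sensitised their skin can be identified by one question before anything is applied. The listed criteria do not ask that question, and such a person may have normal-looking skin on the day of screening.

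What is at stake is an avoidable skin reaction. The subjects are healthy volunteers, and the only benefit that section 4 describes is information for product development. An avoidable harm to an identifiable person is therefore hard to justify, even if it is mild and uncommon.

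**Working it through.** No arithmetic applies. The plan states no figure on this point, so the check is to take one hypothetical volunteer through the criteria and then through the other safeguards. The volunteer has a known earlier reaction to a skin adhesive, intact abdominal skin today, and no other relevant history.

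**Step 1: the exclusions, section 6.3.2 (synopsis identical)**

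| Criterion | Subject matter | Excludes this volunteer? |
|---|---|---|
| 1 | Radio- or chemotherapy, now or in the past 2 months | No |
| 2 | Systemic steroids, or topical steroids around a stoma, now or in the past month | No; it would catch only a reaction recently treated in one of those ways |
| 3 | Pregnancy or breastfeeding | No |
| 4 | Skin problem, peristomal or abdominal | No; worded in the present tense and tied to body area |
| 5 | Other or earlier study participation | No |

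Result: 0 of 5. Both copies of the list run from 1 to 5 with no gap and no redaction mark. Neither contains a general exclusion at the investigator's discretion.

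**Step 2: the visible inclusions, section 6.3.1.** These are consent, age and legal capacity, intact skin, accessible abdomen, pregnancy test and contraception document. The volunteer can meet all of them. Result: 0 of 6 screen for adhesive history.

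**Step 3: does the plan use history elsewhere?** Yes. Exclusions 1 and 2 look back 2 months and 1 month. There is no look-back for the exposure under test.

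**Step 4: the other safeguards, by when they act**

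- Before exposure, on the product: risk assessment and biological safety evaluation of each adhesive (sections 4 and 5.2). These do not use the individual's history.
- After a reaction: the skin is evaluated if complications occur (section 6.4.1), and the subject is withdrawn if safety or well-being is compromised by continuing (section 6.3.4).
- Data checks: concomitant diseases are listed for source verification (section 6.5.1), but nothing links them to eligibility.
- Protocol compliance: section 10 treats enrolment against the criteria as a violation. Enrolling this volunteer breaks no visible criterion, so it would not be flagged.

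**Step 5: extent of exposure.** The maximum number of test products is 6 in section 6.1 and 2 in the synopsis. These passages conflict and must be reconciled. The point does not depend on which applies, because both allow more than one. A pre-stripping adhesive may be added (section 6.4.1).

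**The case against.** The strongest reply is that the remaining risk is already small. Each adhesive is assessed for biological safety, trained personnel apply it, an Ethics Committee approves the plan, and medical care and withdrawal are provided for. Criterion 4 is judged by the investigator, who might read it widely. Section 12 requires that volunteers be told of potential risks and have at least 24 hours to decide, so someone who knows of an adhesive reaction may well decline or mention it. The plan names irritation and mechanical trauma, not allergy, and the order of two items in a sentence is not a ranking.

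Most of this stands, and it keeps the point modest. It does not close the gap. These safeguards act on the product, act after a reaction, or rely on the volunteer or the investigator to raise something that the criteria do not ask about.

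Redaction also limits certainty. Part of the inclusion heading is blacked out, and the note after the exclusions refers to inclusions 5, 6 and 7 although only six are visible. A further inclusion item or a second list is possible. Some baseline-data rows in the section 6.4.3 flow chart are blank, so whether earlier reactions are asked about at baseline cannot be seen. The exclusion lists show no sign of removal.

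A reader might also infer three stronger claims, which the documents do not support:

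- **That sensor readings would be biased.** Nothing visible says that a skin reaction alters measured resistance or shortens wear, and wear time is not visible. Results are reported mainly as summaries and listings (section 7.3), with no pass/fail criterion (section 7.4).
- **That a reactive subject would react at every site.** This needs a component common to all the adhesives, and no composition is given.
- **That the chance of enrolling such a subject can be stated.** The visible text gives neither a sample size nor a prevalence, so any figure would come entirely from assumed inputs.

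**Conclusion.** The concern holds as a subject-safety point about eligibility. On the visible text, a volunteer with a known adhesive allergy or earlier reaction, and currently intact skin, satisfies every listed criterion and may wear more than one new adhesive. None of the visible safeguards screens that person before exposure.

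Its size is the textual count, 0 of 5 exclusions and 0 of 6 visible inclusions, and not a probability. No statistical figure or analysis in the plan is affected. The conclusion assumes that no redacted inclusion item covers adhesive history and that criterion 4 is applied as worded. If either assumption fails, the change below only makes explicit what is already done. The change is worth making because it is cheap and alters who is exposed.

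**What to change.** Add a sixth exclusion to section 6.3.2 and to the synopsis: known hypersensitivity, or a previous skin reaction, to medical, skin or ostomy adhesives. Ask it as one question within the eligibility check that the section 6.4.3 flow chart already places at the baseline visit.

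Keep the wording to reactions that a volunteer can report. A criterion covering any material in the patch or sensor could not be answered for components that have not been disclosed.

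Separately, reconcile the maximum number of test products worn between section 6.1 and the synopsis.

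Cost: one criterion, one question, and a few volunteers who become ineligible. Section 9 counts changes to inclusion criteria as significant; if a new exclusion is treated likewise, it needs a justification, a Change Log entry and, where applicable, notification to or approval by the Ethics Committee before use.

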6.4.3. Flow-chart

Table 1 chart showing the connection between visits and assessments.

	PERFORMED BY	INFOR-MATION VISIT	BASE-LINE VISIT	TERMINATION VISIT
General				
Oral information	Investigator*	X		
Written informed consent	Investigator*		X	
Written informed consent – interview	Investigator*		X	
Signed Secrecy consent	Investigator*			
Documentation for pregnancy test	Investigator*		X	
Check of in- and exclusion criteria	Investigator*		X	
Insurance of subjects well being and compliance with the Evaluation Plan	Investigator*		X	
Registration of baseline data				
Date of birth	Investigator*		X	
Gender	Investigator*		X	
	Investigator *		X	
	Investigator*		X	
	Investigator*		X	
Registration/measurement of end points				
State primary end point	Investigator*			X
Registration of termination				
AEs/ADEs/SAEs/SADEs	Investigator*			X
Termination form	Investigator			X

*Performed by investigator or a trained representative hereof

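### Used as the rule for who is fertile, the 12-month period criterion in 6.3.2 requires no pregnancy test or contraception document from a premenopausal woman whose periods have stopped for a reason other than menopause

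*Combined protocol and SAP*

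**What the plan says.** The note that closes section 6.3.2 states: "Women are considered fertile if they have had a least one period during the last 12 months". No other definition of fertile is visible, and the note does not ask why periods are absent.

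Two inclusion criteria in 6.3.1, repeated in the synopsis, depend on that word:

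- Inclusion 5: "Negative pregnancy test for fertile women".
- Inclusion 6: "Signed document claiming use of safe contraceptives for fertile women".

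The note requires both safeguards together. In addition to the negative test, "the women must also sign a document claiming that they will use safe contraceptives during the study period". The accepted methods are "contraceptive coil, hormone based contraceptives or surgical sterilization". There is one exception. For a woman over 50 who is not yet post-menopausal, the investigator may judge that starting contraception is unreasonable, but must then discuss pregnancy risk with her at inclusion and at each later visit.

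Exclusion 3 covers every subject: "Are pregnant or breastfeeding". Among the baseline documents in 6.4.1 is "Pregnancy test for fertile women and document claiming use safe contraceptives". The flow-chart in 6.4.3 has a row "Documentation for pregnancy test", marked at the baseline visit only, and 6.5.1 lists the pregnancy test among the data points to be verified.

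**The concern.** Absence of periods is used as a stand-in for inability to conceive. The two can differ. On the assumption that hormonal contraceptives and hormonal coils can stop periods, which the documents do not state, a method that the plan accepts can take a woman outside the plan's own safeguards. A premenopausal woman without periods for some other reason is in the same position, and she may be using no accepted method at all.

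The sponsor made pregnancy an exclusion, and section 10 counts enrolment against the criteria as a violation. For these women the visible plan calls for no test result showing that exclusion 3 is met, and no written commitment to contraception while they take part.

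**Working it through.** No arithmetic underlies the definition, and the plan states no figure to reproduce. The check applies the definition in 6.3.2 to different women and reads off what inclusion 5 and 6 then require.

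| Woman | Period in last 12 months | Meets the 6.3.2 definition | Test (incl. 5) | Document (incl. 6) | Exclusion 3 applies |
|---|---|---|---|---|---|
| A. Premenopausal, hormonal method | At least 1 | Yes | Required | Required | Yes |
| B. Premenopausal, same method as A | 0 | No | Not required | Not required | Yes |
| C. Premenopausal, no periods for another reason, no accepted method | 0 | No | Not required | Not required | Yes |
| D. Post-menopausal | 0 | No | Not required | Not required | Yes |

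1. A and B differ only in whether the method has stopped their periods. A must meet both requirements and B neither.
2. The plan does not let contraception stand in for the test: A uses an accepted method and is still tested. So B's use of the same method does not explain why she is exempt.
3. C is treated like D although she is not post-menopausal. Of the four, she has the least protection relative to her need.
4. The over-50 exception does not help B or C. It loosens the contraception requirement for some women and adds nobody to the fertile group.
5. Exclusion 3 covers all four and the criteria are checked at baseline, but the text ties a test to that check only for women classed as fertile.
6. The flow-chart row and the verification item carry no restriction to fertile women. They say where the test is recorded and that it is verified, not who is tested. Read as universal, they would call for a test in men and in post-menopausal women.

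**Size.** Let N be the number of women like B or C. The documents give no basis for N, so the range is 0 to all premenopausal women enrolled. Pregnancy-test documentation is marked at 1 visit, so bringing these women in adds N × 1 = N tests and N × 1 = N signed documents.

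**The case against.** The strongest reply is that the note says 'if', not 'only if'. It names a sufficient condition and never declares anyone not fertile. Its reference to women not yet post-menopausal suggests that menopausal status was in the author's mind, and an investigator remains free to test a woman like B. This stands as far as it goes. A reader might infer that the plan expressly classes such women as not fertile, or that it forbids testing them; the text supports neither. What remains is that this is the only definition staff have, and nothing visible requires the test or the form once a woman fails it.

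A reader might also infer that the baseline list in 6.4.1 confines both items to fertile women. It clearly confines the test. For the document its wording is ambiguous, so the restriction on the document rests on inclusion 6.

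The note also refers to an inclusion 7 that is not visible, and text near the inclusion headings is blacked out. That criterion might deal with the matter. Its content cannot be guessed, so the point is limited to the visible text, and the sponsor can settle it quickly.

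Finally, the consequence is small. A woman like B already uses an accepted method, exclusion 3 still bars pregnant subjects, and sections 4 and 5.2 give the product risks as irritation of the skin and mechanical trauma. This stands and sets the weight of the point. It applies less to a woman like C, who may have no contraception.

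**Conclusion.** The point holds as a cheap improvement. Used as the classification rule, the definition leaves premenopausal women without periods outside the test and the signed document, and treats two women on the same method differently for a reason that does not bear on the purpose of the safeguard.

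It rests on three things: that hormonal methods can stop periods (assumed, not in the documents), that staff use the 12-month sentence as the working rule, and that the unseen inclusion 7 does not already cover these women.

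The impact is minor. A reader might infer that the plan permits pregnant women to enrol, or that the results are at risk. Neither follows: exclusion 3 applies to everyone, and the resistance endpoint and its analysis do not depend on this definition. The number of women affected is unknown and may be zero.

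**What to change.** Keep the definition in 6.3.2 and add directly after it:

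> A woman who is not post-menopausal and has had no period in the last 12 months for another reason (e.g. hormonal contraceptive or hormonal coil) is also considered fertile, unless she has had a hysterectomy; if the reason is unclear, she is treated as fertile.

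Inclusion 5 and 6 and the synopsis pick up the change through the word fertile, as does the test in the baseline list. The default for unclear cases spares staff from having to establish why periods stopped. In the table, B and C move to test and document required, and A and D stay as they are.

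The cost is one baseline pregnancy test and one signed form per affected woman, both already in use in this evaluation. Some women near menopause will be included who do not need it. A woman without periods who uses no accepted method would have to start one or not be enrolled, subject to the existing over-50 exception. If inclusion 7 already covers these women, no change is needed.
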